Study Protocol

Official Title: Simple Non-invasive Breathing Device to Improve Pulmonary Flow Pusability in Single Ventricle Post Fontan

ClinicalTrials.gov ID (NCT number): STUDY22050151

Protocol Date: 1/1/24

Scientific Background

By replicating biphasic ventilation's benefits, Sniff-PEP breathing may prove to improve outcomes in Fontan patients. This research will furnish preliminary data encompassing CMR, biomarker studies, and QoL analyses on Sniff-PEP breathing's effects. With our multidisciplinary team's expertise, we are well-equipped to evaluate this promising intervention, laying the groundwork for broader, multi-institutional research endeavors.

Study Objectives

A. Specific Aims

Aim #1: To evaluate the acute effects of oPEP in Fontan patients undergoing clinically indicated echocardiogram

Hypothesis: oPEP use in Fontan patients will increase flow pulsatility in the inferior vena cava, hepatic veins, Fontan circuit and pulmonary arteries that will ultimately lead to increased cardiac output

Aim #2: To evaluate the effects of one month use oPEP in Fontan patients undergoing clinically indicated echocardiogram

Hypothesis: oPEP use in Fontan patients for a month will increase flow pulsatility in the inferior vena cava, hepatic veins, Fontan circuit and pulmonary arteries that will ultimately lead to increased cardiac output

Study Design & Methods

[name] will be screening pediatric cardiology patients who will be having their appointments in the Lawrenceville locations. Of those patients who meet inclusion criteria, either he, [name], or another appointed official will approach the patient and/or their guardians and discuss the study with them and provide them information. If they agree to participate in the study, then a demonstration will be done for the subject on how to use the device appropriately. The subject will be given their own personal device and will practice the breathing technique for the device. This device has been catalogued, never been used by another person, and sanitized. The patient will place the device between their lips and create a tight seal. Then, they will start by inhaling through their nose and exhaling through their mouth through the device. The subject will practice till they feel comfortable with the breathing maneuver. An initial research quality of life questionnaire will be given to the subject and their guardians for completion. Subject then will have his standard clinic echocardiogram. After completion of the standard echocardiogram protocol, the subject will perform the breathing exercise through the device. While breathing through the device, we will obtain echocardiogram measurements as detailed below:

- a. Subcostal sagittal
- i. Color Doppler of IVC and hepatic veins
- ii. Pulse wave Doppler of IVC (distal to hepatic veins)
- iii. Pulse wave Doppler of hepatic vein

- b. Apical view
- i. 2D of systemic outflow tract
- ii. Color Doppler of systemic outflow tract
- iii. Pulse wave Doppler of systemic outflow tract Doppler
- iv. Continuous wave Doppler of neoaortic valve

- c. Suprasternal coronal Notch view
- i. If possible, 2D of SVC and RPA/LPA junction
- ii. Color Doppler of SVC and RPA/LPA junction
- iii. Pulse wave Doppler of SVC, RPA, and LPA

- d. (if LPA not well seen in suprasternal coronal) Suprasternal sagittal view
- i. Color Doppler of LPA
- ii. Pulse wave Doppler of LPA

These echo measurements will then be confirmed or read by a cardiologist who will be blinded against the condition the patient is in (normal breathing vs breathing through oPEP). 20% of the measurements will be confirmed by another reader.

The patient will complete a brief questionnaire at baseline. We will instruct the patient to use the device 3-4 times daily for a duration of 10-15 minutes. After a period of

approximately 4 weeks, the patient will return to the Lawrenceville location and will have a repeat echocardiogram according to the protocol below:

- a. Subcostal sagittal
- iii. Color Doppler of IVC and hepatic veins
- iv. Pulse wave Doppler of IVC (distal to hepatic veins)
- v. Pulse wave Doppler of hepatic vein

- b. Apical view
- vi. 2D of systemic outflow tract
- vii. Color Doppler of systemic outflow tract
- viii. Pulse wave Doppler of systemic outflow tract Doppler
- ix. Continuous wave Doppler of neoaortic valve

- c. Suprasternal coronal Notch view
- x. If possible, 2D of SVC and RPA/LPA junction
- xi. Color Doppler of SVC and RPA/LPA junction
- xii. Pulse wave Doppler of SVC, RPA, and LPA

- d. (if LPA not well seen in suprasternal coronal) Suprasternal sagittal view
- xiii. Color Doppler of LPA
- xiv. Pulse wave Doppler of LPA

These echo measurements will again be confirmed or read by a cardiologist who will be blinded against the condition the patient is in (normal breathing vs breathing through oPEP). 20% of the measurements will be confirmed by another reader.

At this point, the subject and guardian will be given a follow up questionnaire and we will leave them with the device for their personal use if they choose to keep it.

Otherwise, we will accept the returned device, catalogue return, and will disposed in an appropriate manner.

Eligibility Criteria

Inclusion Criteria:

- Patients with single ventricle with Fontan palliation
- Over the age of 8 years who would be cooperative with breathing through the oPEP device

Exclusion Criteria:

- Patients with Fontan palliation under the age of 8 years
- Patients who have interrupted inferior vena cava

- Patients with abnormal pulmonary artery anatomy

Statistical Considerations

The pulmonary pulsatility index, hepatic vein and portal vein pulsatility index, aortic valve VTI will be compared before and at the time of using the oPEP device. A repeated t-test will be used for within subject comparison. Since this is a pilot study we will plan to include 15 patients.

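### Aim 2 claims a one-month effect of oPEP, but with no control arm or untreated period a 4-week change can be described and not attributed to the device

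*Combined protocol and SAP*

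**What the plan says.** In Study Objectives, the second aim is "Aim #2: To evaluate the effects of one month use oPEP in Fontan patients undergoing clinically indicated echocardiogram". Its hypothesis begins "Hypothesis: oPEP use in Fontan patients for a month will increase flow pulsatility in the inferior vena cava" and extends to the hepatic veins, Fontan circuit, pulmonary arteries and, ultimately, cardiac output.

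Study Design & Methods describes a single group. On the device: "The subject will be given their own personal device and will practice the breathing technique for the device". On the following month: "We will instruct the patient to use the device 3-4 times daily for a duration of 10-15 minutes". After "approximately 4 weeks, the patient will return to the Lawrenceville location and will have a repeat echocardiogram according to the protocol below", a follow-up questionnaire goes to the subject and guardian. No randomisation, control arm, run-in, washout or untreated month is described. The echocardiogram reader is blinded to normal versus oPEP breathing; blinding to visit is not mentioned.

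Statistical Considerations lists the indices and says that these, including "aortic valve VTI will be compared before and at the time of using the oPEP device". The test is given as "A repeated t-test will be used for within subject comparison". No comparison of baseline with 4 weeks is named. On size: "Since this is a pilot study we will plan to include 15 patients".

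**The concern.** The aim and hypothesis are causal: they concern what a month of oPEP does. The design supplies one group measured at two visits, with all members told to use the device in between. Device use and elapsed time are therefore completely confounded. A within-subject comparison across visits can show whether the indices moved, but not why.

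The stated blinding does not help. It protects the acute contrast within a visit, and it cannot separate a month of device use from a month of anything else. The questionnaires have the same limit and a further one, since subjects and guardians know that the device is in use.

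The Background presents this study as groundwork for wider multi-institutional research. If a 4-week rise were taken forward as a sustained device effect, later work would be planned on a claim that this design cannot support.

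**Working it through.** **1. Aim set against design and analysis.**

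| Element | Aim 1 (acute) | Aim 2 (one month) |
|---|---|---|
| Claim | oPEP increases pulsatility and output during use | A month of oPEP increases pulsatility and output |
| Off-device reference | Same patient, same visit | None over the same month |
| Contrast in Statistical Considerations | Before versus at the time of use | Not named |
| Reader blinding | Covers the contrast (breathing condition) | Visit not mentioned |

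The acute aim has a within-patient reference and a stated contrast. The one-month aim has neither an untreated reference nor a named contrast.

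**2. What a non-device drift would do.** The plan's sample size of 15 has no calculation behind it, so there is no figure to reproduce. Variances, alpha and sidedness are also not given. The following is an illustration on these assumptions: a two-sided 5% paired t-test on baseline versus 4 weeks, n = 15, no device effect, and a drift δ in units of the SD of the change. The chance of p < 0.05 comes from the noncentral t distribution with 14 degrees of freedom and noncentrality δ√15 (√15 = 3.873).

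| δ (assumed) | δ√15 | Chance of p < 0.05 |
|---|---|---|
| 0 | 0 | 5.0% |
| 0.10 | 0.387 | 6.5% |
| 0.25 | 0.968 | 14.7% |
| 0.50 | 1.936 | 43.8% |

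The source of the drift is immaterial. A concurrent control would hold the rate at 5% whatever drift the two groups shared.

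**3. Regression to the mean.** For two measurements with equal variance and test-retest correlation r, the expected change is (1 − r) × (distance of the group's mean baseline below the population mean), in SDs of a single measurement. Eligibility rests on Fontan palliation, age, cooperation and anatomy, not on pulsatility or VTI. With no selection on baseline the distance is 0 and so is the expected change. Simulation (20,000 runs, n = 15) gave rejection rates of 4.9%, 5.2% and 5.0% at r = 0.5, 0.7 and 0.9.

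For contrast, suppose that every patient entered below the median, which the documents do not say. The mean baseline is then 0.798 SD low:
- r = 0.5: 0.5 × 0.798 = 0.40 SD; rejection rate 35%
- r = 0.7: 0.3 × 0.798 = 0.24 SD; rejection rate 22%
- r = 0.9: 0.1 × 0.798 = 0.08 SD; rejection rate 10%

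**4. Could the 15 patients support a control?** Assuming two-sided 5% and 80% power, with effects in SDs of the 4-week change, the uncontrolled paired test on 15 detects 0.78 SD. A 7/8 split into device and no-device months detects only about 1.57 SD. Detecting 0.8 SD against a concurrent control takes 26 per arm, or 52 in all.

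**5. What an estimate would look like.** With 15 complete pairs, the 95% confidence interval for the mean change has half-width t(0.975, 14)/√15 = 2.145/3.873 = 0.55 SD of the change.

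**The case against.** The strongest reply is that this is a pilot of 15 meant to give preliminary data, and that an uncontrolled before-and-after design is legitimate for that purpose. A hypothesis is not a conclusion, and the documents contain no rule for reporting or interpreting the 4-week result. This largely stands: a pilot does not need a control arm, and step 4 shows that 15 patients could not support a useful one. It does not remove the point, because an uncontrolled pilot is sound only if its conclusions stay descriptive. The protocol nowhere says that they will, and its Aim 2 wording says the opposite.

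Two stronger readings are tempting and are not supported:
- **A 4-week t-test will be reported as a device effect.** The plan specifies no baseline-to-4-week test. The within-subject t-test sentence follows directly on the acute contrast. The documents show a causal hypothesis with no named analysis and no limit on interpretation, which leaves misattribution open but does not announce it.
- **Regression to the mean will produce a spurious rise.** A reader might infer this because the echocardiograms are clinically indicated. That phrase does not mean that patients are deteriorating. Recruitment is from patients with cardiology appointments, the scan is described as the standard clinic one, and eligibility does not select on the outcomes. Without such selection the expected shift is zero.

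**Conclusion.** The point holds in a limited form. As designed, Aim 2 can describe how the indices change over a month of oPEP use; it cannot show that oPEP changed them. That conclusion follows from the design alone and needs no assumed number.

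The size of any non-device drift cannot be derived from the documents. The rates in step 2 show how a single-arm test would respond to drifts of assumed size, and they do not estimate this study's error rate. Regression to the mean would add to the problem only if baseline scans happened to catch patients at a low point, which the documents do not show. The matter should be corrected because the remedy is nearly free and it prevents an unsound conclusion. It is not a reason to reject a single-arm pilot.

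**What to change.** 1. Reword Aim 2 and its hypothesis along the lines of: *to describe the change in these indices over one month of oPEP use*.
2. In Statistical Considerations, name the Aim 2 contrast: the within-subject change from baseline to 4 weeks, off-device at both visits, reported as an estimate with a 95% confidence interval. Off-device needs saying because the follow-up text does not state which breathing condition is recorded. Setting an on-device 4-week value against an off-device baseline would mix the acute effect into the one-month change. The same signals must be recorded off-device at both visits.
3. State that the 4-week change and the open-label questionnaire changes will not be interpreted as caused by oPEP.

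The cost is mainly wording, plus making sure that the off-device recordings exist at both visits. The downside is a more modest claim for Aim 2; the question of cause is left to a later controlled study.

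### The reader blind for the acute contrast is claimed without a masking method and is at high risk of failing, because device images always form a separate, later block

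*Combined protocol and SAP*

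**What the plan says.** Study Design & Methods sets one order for the baseline visit. First: "Subject then will have his standard clinic echocardiogram". Then: "After completion of the standard echocardiogram protocol, the subject will perform the breathing exercise through the device". The device images have their own list of subcostal, apical and suprasternal views, introduced by "While breathing through the device, we will obtain echocardiogram measurements as detailed below". No view list is given for the normal-breathing study.

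The blind follows directly: "These echo measurements will then be confirmed or read by a cardiologist who will be blinded against the condition the patient is in", with the two states named as "normal breathing vs breathing through oPEP". The same assurance is repeated for the four-week visit. On the second reader, the text says "20% of the measurements will be confirmed by another reader".

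Statistical Considerations defines the comparison that this reading feeds. Pulsatility indices (pulmonary, hepatic vein and portal vein) and aortic valve VTI "will be compared before and at the time of using the oPEP device". The test is "A repeated t-test will be used for within subject comparison", with 15 patients.

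**The concern.** A blind to breathing state needs some step that separates the image from the circumstances in which it was taken. The plan describes none, and its acquisition sequence works against the claim. Every device image is later than every normal-breathing image from that visit, and belongs to a limited list instead of the standard study.

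The wording weakens the blind further. Confirming a number that someone else has already produced is not an independent masked measurement, and whoever acquired the images knew the state. The second reader also only confirms, and the text does not say whether that reader is masked.

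The stakes are highest for the acute contrast. It is the only comparison that Statistical Considerations explicitly defines. Each patient serves as their own control, and the hypothesis under Specific Aims is directional (more pulsatility on the device). Masked reading is the only protection against measurement bias that the plan names. Where an index depends on which beats or which points of a trace are measured, a reader who knows the state can favour the expected direction without intending to. A paired t-test cannot separate that shift from a device effect.

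**Working it through.** **Step 1: what the text fixes and what it leaves open.**

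| Item | What the protocol gives |
|---|---|
| Order of states at baseline | Fixed: standard echocardiogram, then device; no counterbalancing |
| Views, normal breathing | Standard clinic study; no list |
| Views, device breathing | Limited list, items a to d |
| Blind | Asserted for normal versus oPEP breathing |
| Masking method | None stated: no removal of time or labels, no clip extraction, no shuffling |
| How a value arises | Confirmed or read; who makes the initial measurement is not stated |
| Beat selection | No rule |
| Storage and presentation to the reader | Not stated |

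The first three rows mean that images presented as acquired would show the state by position and time. The remaining rows mean that nothing in the plan ensures they are presented otherwise. There is a further ambiguity. The sentence on blinding refers back to measurements listed only for device breathing, so the text does not make clear that normal-breathing measurements go through the same masked read.

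**Step 2: scale, for illustration.** The plan has no figure to reproduce here. The 15 patients are justified only as a pilot, and no alpha, sidedness, power, effect size or SD is given.

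Inputs: n = 15 from Statistical Considerations; two-sided alpha of 5%, assumed; no true device effect; a systematic reader shift of b SDs of the paired difference, assumed.

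With 14 degrees of freedom the critical value is c = 2.145. The paired t statistic then follows a noncentral t distribution with noncentrality b × √15, so

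P(reject) = 1 − F(c; 14, b√15) + F(−c; 14, b√15).

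| Bias b (SD of paired difference) | Noncentrality b√15 | P(reject) with no true effect |
|---|---|---|
| 0 | 0 | 5.0% |
| 0.1 | 0.387 | 6.5% |
| 0.2 | 0.775 | 11.2% |
| 0.3 | 1.162 | 19.2% |

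These rates apply to each test separately. For comparison, the same formula gives 80% power at a true effect of about 0.78 SD, so the shifts shown are well below what the study could reliably detect.

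**The case against.** The strongest reply is that acquisition order is not reading order. The protocol asserts the blind at both visits, and silence about method does not show that it fails. The team may already intend to extract clips, strip them and shuffle them, and nothing in the text excludes this. That stands. A reader might infer that the blind simply does not hold, but the documents do not support that conclusion.

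Two related inferences also go too far. A reader might assume that both blocks are stored in a single echo study, so that opening it gives the state away. The text shows the same visit and direct succession, and says nothing about storage. A reader might also assume that the Doppler trace itself betrays device breathing. That is plausible, but the protocol gives no breathing rate or waveform description. Likewise it gives no formula for the pulsatility index and does not say that the reader chooses the beats, so the route by which bias would enter is reasoned and not documented.

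Finally, the illustration rests on an assumed bias and an assumed alpha. At 0.1 SD the inflation is small, so the figures do not show that the bias is material.

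None of this supplies the missing method. The claim of blinding still has nothing behind it in the plan, and the option merely to confirm values is in the text itself.

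**Conclusion.** The point holds in this form: the blind to breathing state is claimed without a method, the fixed block order exposes it, and the option to confirm weakens it further. It is at high risk of failing for the acute contrast; the documents do not establish that it fails.

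The size of any bias cannot be derived from the plan. Under the assumptions stated above, the false-positive rate of each test would move from 5% to about 6.5%, 11% or 19% for a bias of 0.1, 0.2 or 0.3 SD. The change is worth making because it is cheap and protects the plan's only named safeguard against measurement bias. The four-week visit carries the same unsupported assurance, but the order of acquisition there is not stated, so the argument from block order is confined to baseline.

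**What to change.** Add a short reading procedure to Study Design & Methods:

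1. Acquire the same Doppler views, for the analysed indices, in both breathing states.
2. Export those clips stripped of time, sequence, annotation and any existing measurements.
3. Have the existing cardiologist measure them, not confirm them, in computer-shuffled order. Do the 20% second reads from the same masked clips.
4. Fix beat selection in advance so that it depends on neither the state nor the reader. For example, compute each index per beat and average over the same number of consecutive beats, or over the same recording duration, in each state. Avoid taking extremes over an equal number of respiratory cycles: if breathing is slower on the device, the device window would be longer, and a maximum-minus-minimum index would tend to widen for that reason alone.
5. Because the trace may still reveal the state, describe the reading as order-masked with fixed beat selection, not as fully blinded.

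The cost is data handling for 15 patients and a slightly weaker blinding claim. No extra reader is needed. If the standard clinic study lacks some of the listed views, a few more normal-breathing images would be required; the protocol does not say whether it does. Masked reading would not remove the separate confounding of breathing state with time that comes from always imaging the device second.

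### Recent device use is neither controlled nor recorded at the baseline and 4-week echoes, so a resting change over the month cannot be assigned to Aim 2 rather than to unequal recent exposure

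*Combined protocol and SAP*

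**What the plan says.** All references are to the combined protocol and SAP.

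- **Study Objectives, A. Specific Aims.** Aim 1 is "To evaluate the acute effects of oPEP in Fontan patients undergoing clinically indicated echocardiogram". Aim 2 is "To evaluate the effects of one month use oPEP in Fontan patients undergoing clinically indicated echocardiogram", with the hypothesis that "oPEP use in Fontan patients for a month will increase flow pulsatility". The two are posed as different questions.
- **Study Design & Methods, first visit.** The order is demonstration, practice, questionnaire, standard clinic echo, then the echo on the device. On practice: "The subject will practice till they feel comfortable with the breathing maneuver". No length is given, and no interval before the standard echo. For the last step: "While breathing through the device, we will obtain echocardiogram measurements as detailed below".
- **Study Design & Methods, home use.** "We will instruct the patient to use the device 3-4 times daily for a duration of 10-15 minutes". There is no separate provision for the day of the return visit.
- **Study Design & Methods, return visit.** After "approximately 4 weeks, the patient will return to the Lawrenceville location and will have a repeat echocardiogram according to the protocol below". The list of views that follows does not say whether they are taken at rest, on the device, or both. Only the blinding sentence ("These echo measurements will again be confirmed or read by a cardiologist who will be blinded against the condition the patient is in") implies both.
- **Statistical Considerations.** The stated comparison is of indices before and during device use, by a within-subject t-test, in 15 patients. No contrast between baseline and week 4 is defined.

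No section mentions a diary or a field for the time of last use. The contents of the two questionnaires are not given.

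**The concern.** A patient may arrive at week 4 minutes after a session, or not having used the device since the previous evening. If a session leaves a short-lived change in venous or pulmonary flow, the first patient carries it into the resting images and the second does not. The same applies at baseline, where practice comes shortly before the standard echo.

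There is no control arm, so nothing else in the design separates a month's effect from the residue of a recent session. Blinding the reader to the breathing condition does not help, because a residue would be present in normal-breathing images too. If the time of last use is not captured at the visit, no later analysis can recover it. What is at stake is whether Aim 2 can be told apart from Aim 1. Uneven timing would also add noise to the 4-week change.

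**Working it through.** **1. What the contrast estimates.** Let M be the effect of the month on resting indices. Let R0 be the residue of practice at the baseline scan, and R4 the residue of the last session at the week-4 scan.

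- Baseline, resting: underlying level + R0
- Week 4, resting: underlying level + M + R4
- Difference: M + (R4 − R0)

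The difference equals M only if R4 = R0. The protocol fixes neither term. If R4 exceeds R0, the month's effect is overstated. If practice immediately before the baseline scan leaves the larger residue, it is understated.

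**2. How recent the last home session is likely to be.** Input from the protocol: 3-4 sessions a day. Assumptions: about 15 waking hours, even spacing, full adherence, a visit at a random time in the waking day.

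- Spacing: 15/3 = 5 h; 15/4 = 3.75 h
- Mean time since last session, half the spacing: 2.5 h; 1.875 h, about 1.9 h

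The range runs from 0 to about 5 h, or overnight for an early slot. At baseline the interval after practice is not stated; only a questionnaire is listed between practice and the echo, so it may well be shorter.

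**3. What a net residual would do.** The plan's 15 patients come with no alpha, power, effect size or SD, so there is no figure to reproduce. Assumptions for illustration: paired t-test, n = 15, 14 degrees of freedom, two-sided alpha 0.05 (critical value 2.145), M = 0, and a constant net residual d = R4 − R0 in SD units of the paired difference. The rejection probability comes from the noncentral t distribution with noncentrality d × √15; for d = 0.4 this is 0.4 × 3.873 = 1.55.

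| Net residual d (SD) | Chance of a significant 4-week change when M = 0 |
|---|---|
| 0 | 5% |
| 0.2 | 11% |
| 0.4 | 30% |
| 0.5 | 44% |
| 0.8 | 82% |

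Put another way, if the acute effect were 0.8 SD and a net 25%, 50% or 75% of it persisted, d would be 0.2, 0.4 or 0.6, giving 11%, 30% or 58%.

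**4. The other direction.** The table is symmetric: a negative d gives the same chances of a significant fall. A negative d can also hide a real effect. With M = 0.8 SD and d = −0.4 SD, the shift left is 0.8 − 0.4 = 0.4 SD, and power drops from 82% to 30%.

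Every value of d here is an assumption; the documents supply none.

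**The case against.** **Aim 2 does not say lasting.** A reader might infer that Aim 2 asks for a sustained effect and that any residue is contamination. The text says only the effect of a month of use. An on-treatment reading, in which residual benefit from regular sessions is part of the effect, is also fair. This stands. It changes how the result should be described, but not the need to know how recent the exposure was.

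**No after-effect is shown.** The acute effect is measured while the patient is breathing through the device, and nothing in the documents says that it outlasts the session. This stands: the bias is possible, not demonstrated.

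**Bias in favour of the device.** A reader might infer that a raised week-4 index could simply be the tail of that day's session. The documents do not support that one direction, because baseline also follows device use and its residue could cancel or reverse the bias.

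**Repairing week 4 alone.** Moving only the week-4 scan ahead of that day's use, with baseline left after practice, would create a systematic difference in recent exposure. It is also tempting to allow a claim of sustained effect only if it appears in patients scanned before any use that day. That subset would be small and self-selected. At a true 0.8 SD under the same assumptions, power is about 28% with 5 such patients and 43% with 7, against 82% with 15. Without a definition of what counts as appearing, the rule cannot be applied either.

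**A larger gap lies upstream.** The week-4 breathing condition and the Aim 2 contrast are themselves undefined. This stands, and the fix should cover both. Defining a resting-to-resting contrast would not by itself remove the residue, however. If week-4 images on the device were compared with a resting baseline, the acute effect would enter directly.

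**Conclusion.** The point holds as a gap in attribution. The protocol poses an acute and a one-month question, but neither controls nor provides for recording recent device use at the two scans that a resting one-month comparison would rest on. If there is any short-term after-effect, the difference between the scans is the month's effect plus an unknown difference in residue.

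The size cannot be fixed from the documents. With no after-effect, or equal residue at both scans, the bias is nil. Under the stated assumptions, a net residual of 0.4 SD would raise the chance of a spurious significant change from 5% to 30%, and the same residual in the opposite direction would cut power for a true 0.8 SD effect from 82% to 30%. The 1.9-2.5 h average interval rests on assumed even spacing over 15 waking hours. That the time of last use goes uncaptured is inferred from the protocol's silence; the follow-up questionnaire might ask for it.

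The repair is cheap and cannot be made after the data are collected, so it is worth making even in a 15-patient pilot.

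**What to change.** 1. At both visits, acquire the normal-breathing Doppler set before any device use at the clinic. At baseline this means before the practice session.
2. At week 4, record the clock time of the last device session and of the echo.
3. State the breathing condition for each week-4 image set. In Statistical Considerations, define the Aim 2 contrast as normal breathing at week 4 versus normal breathing at baseline, separate from the comparison of before and during device use that serves Aim 1.
4. List time since last use for each patient beside the individual change. Describe the result as an effect of one month of use that may include residual acute effect where the last session was recent.
5. Do not make the claim depend on the subset scanned before any use that day.

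These steps make baseline free of same-day practice and make recent exposure at week 4 visible; they do not remove a residue at week 4. Whether to give patients any instruction about device use on the visit day is for the investigators to decide.

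The cost is one extra form field and a fixed imaging order, with practice moved after the normal-breathing images at the first visit. No extra scan, staff or patients are needed.

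### Echo readers are blinded to breathing state only and may confirm rather than measure, so a baseline versus 4-week comparison for Aim 2 has no stated masking to visit

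*Combined protocol and SAP*

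**What the plan says.** **Baseline visit (Study Design & Methods).** The order is "Subject then will have his standard clinic echocardiogram", followed by the device: "While breathing through the device, we will obtain echocardiogram measurements as detailed below". The results are then to be "confirmed or read by a cardiologist who will be blinded against the condition the patient is in (normal breathing vs breathing through oPEP"). A second check follows: "20% of the measurements will be confirmed by another reader".

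**4-week visit (same section).** The patient returns and "will have a repeat echocardiogram according to the protocol below". The reader sentence is repeated: "These echo measurements will again be confirmed or read by a cardiologist who will be blinded against the condition the patient is in", with the same bracketed definition of the condition. The 20% check is repeated too. The breathing state during this echocardiogram is not given.

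**Study Objectives, Aim #2.** The hypothesis is directional: "oPEP use in Fontan patients for a month will increase flow pulsatility".

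**Statistical Considerations.** One contrast is named. The pulsatility indices and "aortic valve VTI will be compared before and at the time of using the oPEP device", by a within-subject t-test in 15 patients. No baseline versus 4-week contrast is defined.

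**The concern.** The masking was built for the acute question and carried over unchanged to a visit that serves a different one. A reader who cannot tell normal from device breathing may still know which study came after a month of use. There is no control group for the one-month effect, and the plan predicts its direction. Masking to visit is therefore the main protection against reader expectation in a baseline versus 4-week comparison, and it is not stated.

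Two features of the reading rule add to this.

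- The cardiologist may confirm instead of measure. Whoever obtains the on-device measurements can see both the device and the visit. If a value is recorded at that point, confirming it keeps a number that was not formed blind, however well the confirmer is masked. This would touch the acute comparison as well.
- The 20% check is also only a confirmation. Independence from the first value is not required, and agreement judged with sight of that value can look better than it is.

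The documents do not say that readers will know the visit or see earlier values. Their wording allows it.

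**Working it through.** **1. Masking against contrast.** The plan has two reader-masking statements, one per visit.

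| Contrast | Where it arises | Masking needed | Masking stated |
|---|---|---|---|
| Before versus during device use | Statistical Considerations; Aim #1 | Breathing state | Yes, unless values recorded unblinded are merely confirmed |
| Baseline versus 4 weeks | Implied by Aim #2; not defined in Statistical Considerations | Visit and date | No |

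The plan also does not mention random reading order, joint reading of the two visits, or masking of the second reader.

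**2. Is there a figure to reproduce?** No. The documents give no alpha, sidedness, SD, effect size or reader variability, and the sample size is justified only as a pilot. What follows illustrates sensitivity; it does not estimate the bias.

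**3. Effect of a reader shift on the false-positive rate.**

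Inputs:
- n = 15 and a within-subject t-test, from Statistical Considerations.
- Assumed: two-sided alpha 5%, no true effect, and a constant reader shift δ between visits, in units of the SD of the paired difference.

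Formula: the test statistic follows a noncentral t distribution with df = 15 − 1 = 14 and noncentrality δ × √15 = δ × 3.873. The false-positive rate is the probability that it falls outside the two-sided 5% critical values of the central t on 14 df.

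| Shift δ (SD) | Noncentrality | False-positive rate |
|---|---|---|
| 0 | 0 | 5.0% |
| 0.1 | 0.387 | 6.5% |
| 0.18 | 0.697 | 10% (double the nominal rate) |
| 0.2 | 0.775 | 11.2% |
| 0.3 | 1.162 | 19.2% |
| 0.5 | 1.936 | 43.8% |

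Simulation with 400,000 trials per shift gave 11.1% at 0.2 SD and 19.2% at 0.3 SD, in agreement.

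**4. Reading load if everything is measured afresh**, with all 15 patients completing:
- Baseline: 15 normal-breathing + 15 on-device = 30 image sets.
- 4 weeks, one breathing state: 30 + 15 = 45 in total.
- 4 weeks, both states: 30 + 30 = 60 in total.

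**The case against.** The strongest reply is that the harm falls on a contrast the plan does not contain. Statistical Considerations names only the before-versus-during comparison, and the stated blinding fits it. The root gap is then the missing Aim #2 analysis. The 4-week text also repeats the two breathing states, so both might be imaged again and compared within that visit, in which case masking to visit would matter little.

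This narrows the point without removing it. Aim #2 concerns a month of use, and the natural evidence for it is the change from baseline. Masking has to be arranged before images are read; an analysis defined later cannot restore it.

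Second, the argument about confirming is conditional. The baseline list consists of views and Doppler acquisitions, not numerical values. No text says that a value is recorded at acquisition, or that the second reader sees the first value. That stands: this is an ambiguity that permits a problem, not proof of one.

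Third, masked reading does not deal with change over time, or with acquisition by staff who know the visit and the breathing state. That is also correct. The proposed change protects the reading step only.

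Fourth, the illustrative shifts are assumed and applied to a test not planned for this contrast, so they should not carry the weight of the point. They do not; the point rests on the text.

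**Conclusion.** The concern holds. Both reader sentences confine the blinding to breathing state and allow confirmation in place of measurement. No text supplies masking to visit or date, or requires an independent second reading.

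The acute comparison is covered, unless unblinded values are recorded and then confirmed. A baseline versus 4-week comparison is not covered.

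The bias cannot be sized from the documents. Under the assumptions stated in the calculation, shifts of 0.2 to 0.3 SD are enough to double the nominal error rate or more, whereas a shift of 0.1 SD hardly matters. The change should be made, with medium confidence: the omission is clear in the text, but whether readers would in practice know the visit is not.

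**What to change.** In Study Design & Methods, replace the two reader sentences at both visits with:

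> The blinded cardiologist will measure all study images afresh from stored images, without sight of earlier values, with visit and date as well as breathing state masked, and with baseline and 4-week images read together in random order. A random 20% of measurements will be independently re-measured by the second reader without sight of the first values.

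This does not define the Aim #2 contrast, which Statistical Considerations must state separately.

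**Cost.**
- Someone other than the readers must relabel and shuffle the images. Hiding breathing state already calls for some such step.
- The cardiologist already named must measure at most 45 or 60 image sets, depending on the 4-week breathing state, including the baseline standard-echo images.
- Research reads wait until the 4-week images exist.
- The change assumes that images are stored, which the documents do not say and the sponsor should confirm.

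Both reader roles are already in the plan, so no new reader is needed.
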